#### Exclusion Criteria

Subjects will not be eligible for participation if they meet one or more of the following exclusion criteria:

- Report citrus allergies.
- Report a history of cardiovascular disease, diabetes, or cancer
- Subjects who have evidence of hepatic disease or dysfunction, e.g. ALT, or alkaline phosphatase twice the upper limit of normal; hepatitis; jaundice; cirrhosis.
- Current pregnancy or breastfeeding
- Women of childbearing potential who are not using an effective method of birth control (i.e., barrier method, intrauterine and cervical devices, oral contraceptives, hormonal injections (Depo Provera®), condoms with spermicidal gel or foam, contraceptive patch (Ortho Evra), diaphragm, or abstinence), are not surgically sterilized (including tubal ligation and hysterectomy), or not at least two years postmenopausal. All women of childbearing potential will have a pregnancy test performed prior to starting the study treatment in each cohort. If a subject becomes pregnant during the study, they will be dropped from the study.
- Chronic use of medications except over the counter medications and supplements that have been stopped 72 hours prior to the test day.
- Reported clinically significant GI malabsorption syndromes such as chronic diarrhea, celiac disease or malabsorption from bariatric surgery within one month of the study.
- Clinically significant abnormal laboratory markers (as determined by the medical investigator).
- Subjects with anticipated surgery during the study period.
- Subjects with a reported history of substance abuse or alcoholism or significant psychiatric disorder that would interfere with the ability to complete the study.
- Subjects who have donated blood during the month prior to study entry or planned during the study.
- Subjects who have participated in other studies using an investigational drug during the preceding three months.
- Subjects who are current smokers or have smoked within the previous three months. Smoking is not permitted during the study.

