#### **Recruitment and Screening**

Subjects will be recruited through the use of printed material, targeted solicitation through the Pennington Biomedical Center email listserv and social media. The Pennington recruiting department will screen potential subjects over the phone, and those meeting basic eligibility criteria (age, self-reported BMI, medical and medication history) will be scheduled for a screening visit.

Subject eligibility criteria will be evaluated at a single screening visit. The screening visit will occur in the outpatient clinic, in the morning following confirmation of an overnight (at least 8 hours) fast. Subjects who provide informed consent will proceed with the tests and measurements of the screening visit. Subjects who satisfy the eligibility criteria will be enrolled in a study cohort. The schedule of assessments is provided in Table 2.

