### Randomization Procedure and Blinding

Each subject in the cohorts will be randomly assigned one of the relevant treatment sequences in order of enrollment. Treatment sequence assignments will be balanced so that each sequential block will have unique treatment sequences. As an example, the first three enrolled subjects in each cohort will be randomly assigned to one of three distinct treatment sequences, as will enrollees 4-6 and 7-9. As a result, three of the nine subjects in each cohort will be randomly assigned to each of the three treatment sequences. The randomization scheme will be prepared by [name] under the supervision of [name]. Except for the pharmacist who will prepare and dispense the capsules, all study staff and the investigators will be blinded to the randomization.

Table 2. Schedule of Assessments

	Screening	Visit 1a	Visit 1b	Visit 2a	Visit 2b	Visit 3a	Visit 3b
Consent	x						
Height	x						
Weight	x	x		x		x	
Blood Pressure/Pulse/Temperature	x	x		x		x	
Medical History Questionnaire	x						
Pregnancy Test (Urine)*	x						
Concomitant Medications	x						
Chemistry Panel/CBC	x						
Adverse Events		x	x	x	x	x	x
Plasma naringenin			x			x	x
Chemistry Panel/CBC (0 hr)**		x		x		x	
Chemistry Panel/CBC (24 hrs later)**			x		x		x
Naringenin Administration		x		x		x	
IV Placement		x					
Blood Collection at 0, 2, 3, 3.5, 4, 4.5, 6, 8, and 12 hours		x					

\* Women of Child bearing potential

\*\* For Cohort 2 only BUN, AST, and Bilirubin added to Chem 15 panel

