#### Screening Visit (1½ hours)

Subjects will report to Pennington Biomedical in the morning following an overnight fast (except for water) that began no later than 8 hours prior to the study appointment. The screening visit includes explanation of the study purpose, procedures, and signing of the informed consent. If the participant agrees to participate by signing a consent form, the following tests and measurements will be performed:

- Self-report of personal and family medical history.
- Height, weight, vital signs (blood pressure, pulse, and temperature).
- Concomitant medication use.
- Urine specimen collection for urine human chorionic gonadotropin (HCG) (for pregnancy in women of child bearing potential).
- Blood collection for complete blood count (CBC) and Chemistry 15 panel.

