**Visit 1b (½ hour, fasting for at least 8 hours)**

- Subjects will return 24 hours post naringenin administration and blood will be drawn for CBC, Chemistry 15 panel, and to evaluate serum naringenin concentrations.
- Adverse events will be assessed 24 hours after naringenin dosing.

Subjects will return to the clinic to complete Visit 2 no less than seven days after the completion of Visit 1.

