**Visit 2b (½ hour, fasting for at least 8 hours)**

- Subjects will return 24 hours post naringenin administration and blood will be collected for CBC, and Chemistry 15 panel.
- Adverse events will be assessed 24 hours after naringenin dosing.

Subjects will return to the clinic to complete Visit 3 no less than seven days after the completion of Visit 2.

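### The only scheduled pregnancy test is at screening, yet dosing spans at least 16 days and each cohort's higher dose always falls at Visit 2 or 3

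*Combined protocol and SAP*

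**What the plan says.** The Exclusion Criteria rule out current pregnancy at entry. They also exclude "Women of childbearing potential who are not using an effective method of birth control", with surgical sterilisation and established menopause as the alternatives. On testing they state: "All women of childbearing potential will have a pregnancy test performed prior to starting the study treatment in each cohort". On what follows a pregnancy: "If a subject becomes pregnant during the study, they will be dropped from the study". The Data Safety Monitoring Plan lists pregnancy among the grounds for breaking an individual subject's blind.

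Table 2 marks the urine pregnancy test once, in the Screening column, for women of childbearing potential. The Screening Visit is the only visit whose procedure list includes hCG. The lists for Visits 1, 2a and 3a name weight, vital signs, blood tests and dosing, but no pregnancy test. Cohort 2 differs only in dose and in three added chemistry analytes.

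On timing, Recruitment and Screening says "Subject eligibility criteria will be evaluated at a single screening visit". Visit 1b says "Subjects will return to the clinic to complete Visit 2 no less than seven days after the completion of Visit 1", and Visit 2b says "Subjects will return to the clinic to complete Visit 3 no less than seven days after the completion of Visit 2". Both intervals are minimums. Neither has an upper limit, and no interval is given between screening and Visit 1.

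**The concern.** The plan treats pregnancy as incompatible with dosing, but after screening no scheduled procedure can bring the drop rule into play. It works only if the subject knows that she is pregnant and says so. The example questions under Adverse Events ask how she feels, about medical problems and about new medicines. They do not ask about pregnancy, and no visit list re-checks contraception.

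What is at stake is participant safety in a trial whose primary objective is safety and tolerability. A woman who conceives after screening could be given one or two active doses under the blind with no deviation from the schedule. The trial's estimates and conclusions are not at stake.

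**Working it through.** **Is there a contradiction?** No. Each cohort has its own nine subjects, 18 in all, so one test at screening does precede treatment in each subject's cohort. The eligibility wording is met. If that wording were read as asking for a test on the day of the first dose, Table 2 and the Visit 1 list do not schedule one, and Visits 2 and 3 would still have none.

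**Minimum timing.** Take the first administration as day 0. Each visit is completed by its 24-hour return (Visits 1b and 2b), and the next dosing visit is at least 7 days later.

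- Second administration: 0 + 1 + 7 = day 8 or later.
- Third administration: 8 + 1 + 7 = day 16 or later.

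If completion is taken to mean the dosing day itself, the days are 0, 7 and 14. The time from screening to Visit 1, which is not specified, is added in either case.

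**Doses by visit**, from Table 1 with three subjects per sequence:

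| Visit | Earliest day | Active | Placebo | Higher dose of the cohort (300 or 900 mg) |
|---|---|---|---|---|
| 1 | 0 | 12 (sequences 1, 2, 4, 5) | 6 | 0 |
| 2 | 8 | 12 (sequences 2, 3, 5, 6) | 6 | 6 (sequences 2, 5) |
| 3 | 16 | 12 (sequences 1, 3, 4, 6) | 6 | 12 (sequences 1, 3, 4, 6) |
| Total | | 36 | 18 | 18 |

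- Active doses at Visits 2 and 3: (12 + 12)/36 = 24/36 = 67%.
- Active doses at Visit 3: 12/36 = 33%.
- The 900 mg dose alone: 3 at Visit 2 and 6 at Visit 3.

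**Who is concerned.** Only women of childbearing potential, whose number the documents do not give. It can lie between 0 and 18. At two active doses each, between 0 and 36 active doses have no repeat test before them. If half of the subjects are such women (an assumption), the figure is 9 × 2 = 18. These are counts of doses, not of expected pregnancies. The documents give no pregnancy rate, so no probability is estimated.

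**The case against.** The strongest reply is that the sponsor has chosen a testing frequency and met it, and that several safeguards surround it: exclusion of pregnancy, required contraception, a screening test, adverse-event enquiry at all six study attendances, a drop rule, and unblinding for pregnancy. Exposure is two single doses of a food component that is sold as a supplement, with a reported half-life of about 2.3 hours. No reproductive hazard is documented. All of this stands, and it limits the weight of the point. It does not supply a means of detecting a pregnancy that begins after screening. The plan itself did not treat contraception as enough, since it added a test and a drop rule.

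A second reply is that a later, larger dose is simply what an ascending design does, and that 600 mg is given at Visit 1 in sequences 4 and 5, twice Cohort 1's higher dose. That is correct. The position of the higher dose shows how far it lies from the only test, and nothing about reproductive risk.

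A third concerns detection lag. Suppose that a urine test turns positive L days after conception; the documents give no value for L. At minimum spacing, if L exceeds 8, the Visit 2a test cannot detect a conception that follows Visit 1a. If L exceeds 16, the Visit 3a test cannot either. This limits what the later tests achieve when visits run at minimum spacing. They still help with conceptions between screening and Visit 1a, and with longer gaps between visits, which the plan allows without limit.

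Finally, the 16-day span depends on the 24-hour return completing a visit. That is the natural reading, because the 7-day rule is stated under Visits 1b and 2b. The looser reading gives 14 days and the same conclusion.

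**Conclusion.** The point holds. It is a gap in the schedule and does not contradict the eligibility text. With testing at screening only, the rule to drop a pregnant subject relies on self-report throughout a dosing period of at least 16 days (14 on the looser reading), plus an unlimited wait after screening. The counts of doses follow directly from Table 1. The share that concerns women of childbearing potential is unknown.

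The event is unlikely and no hazard is documented, so this is a low-cost safety improvement that should be made. It does not bear on the validity of the trial: endpoints, analysis, sample size and escalation rules are untouched.

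**What to change.** In Table 2, mark the existing urine hCG test at Visits 1a, 2a and 3a for women of childbearing potential. Add a matching line to the procedure lists for Visits 1, 2a and 3a, stating that the result is read before the capsule is given. If the result is positive, give no capsule and apply the existing drop rule. Cohort 2 takes over the change because its visits follow those of Cohort 1. The Visit 1a test also covers the open interval after screening as far as pregnancy is concerned, so no repeat screening visit is needed.

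The cost is at most 18 × 3 = 54 urine tests, if every subject were a woman of childbearing potential, or 9 × 3 = 27 if half are (an assumption). Men are also eligible, so the true number should be below the maximum. Dosing waits for the result, which I assume takes a few minutes. Urine collection is already part of the study and the Risks/Benefits section attaches no risk to it, so no new staff or invasive procedure is required.

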## STUDY DESIGN

This is a placebo-controlled, ascending treatment crossover design trial with washout periods of at least one week.

**Primary objective:** Evaluate the effect of single oral administration of naringenin at four escalating doses on safety and tolerability in healthy volunteers.

**Secondary objective:** Evaluate the pharmacokinetics of naringenin at low (150 mg) and high (600 mg) doses to test if changes in serum concentrations are proportional to the dose, by assessing naringenin drug exposure ( $AUC_{0-24}$ ).

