**Study Subjects**

This study will enroll 18 healthy adult male and female subjects. Subjects will be enrolled on the basis of the following eligibility criteria:

Inclusion Criteria

- Adult (≥18 years)

- Body mass index (determined at the screening visit) between 20 and 35 kg/m^2
- No evidence of diabetes (fasting blood sugar <126 mg/dL)
- Willing to refrain from consuming citrus fruits and tomato in any form, for 36 hours prior to each test day. Subjects will be provided a list of foods to avoid (Appendix I).

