## **STATISTICAL CONSIDERATIONS**

As comparative efficacy of the doses of the extract is not the primary issue in this protocol, power to detect efficacious effects is not specifically evaluated to justify sample sizes. A sample of 18 subjects (three subjects in each of three treatment sequences in each of two cohorts) will be enrolled in the ascending single dose evaluation. Thus, all nine subjects in Cohort 1 will receive the placebo and both 150 and 300 mg doses of the extract; similarly all 9 subjects in Cohort 2 will receive the placebo and both 600 and 900 mg doses of the extract. Before the next cohort is commenced, subjects in the preceding cohort must have received all three treatments and the safety and tolerability data must have been assessed showing tolerance to the doses of naringenin. Based on the pharmacokinetic study done in humans, the sample size (n=6, at each dose) is sufficient to provide a pharmacokinetic profile of naringenin in serum.

The primary outcome will be to determine the effect of the naringenin extract on safety and tolerability based on clinical and biochemical assessment.

The secondary outcome will be to determine the pharmacokinetics of naringenin at the 150 mg and 600 mg doses. Serum concentrations of naringenin will be obtained to assess drug exposure.

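### The one-month window in the malabsorption exclusion has unclear scope, and on every reading it admits people with older bariatric surgery who report no significant malabsorption

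*Combined protocol and SAP*

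**What the plan says.** Under Exclusion Criteria, the relevant item opens with "Reported clinically significant GI malabsorption syndromes such as chronic diarrhea" and its list of examples ends with "celiac disease or malabsorption from bariatric surgery within one month of the study".

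The only criterion about surgery as such looks forward: "Subjects with anticipated surgery during the study period". The inclusion list accepts "Body mass index (determined at the screening visit) between 20 and 35 kg/m"². The Study Subjects section describes the population with "This study will enroll 18 healthy adult male and female subjects".

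The secondary objective under Study Design is to "test if changes in serum concentrations are proportional to the dose", judged by AUC0-24 at 150 mg and 600 mg. Statistical Considerations states that "the sample size (n=6, at each dose) is sufficient to provide a pharmacokinetic profile of naringenin in serum", citing the earlier human pharmacokinetic study. The Rationale for Naringenin Dose describes that study's six participants as being in good health.

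**The concern.** The criterion is evidently meant to keep out people who absorb abnormally. Elsewhere in the same list, lasting conditions (cardiovascular disease, diabetes, cancer) carry no time limit, while short look-backs go with passing exposures such as blood donation, other investigational drugs and smoking. Bariatric surgery leaves a lasting anatomical change, and the protocol itself names it as a cause of malabsorption. Yet it sits beside a one-month limit for which no reason is given.

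Cmax, Tmax, AUC0-24 and apparent clearance (Dose/AUC) after an oral capsule all depend on absorption. Table 1 puts 150 mg in Cohort 1 and 600 mg in Cohort 2, so no one serves as their own control across these two doses. A subject with altered absorption would change one group's mean only, and this would look like a departure from proportionality.

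**Working it through.** **Who is eligible.** Three attachments of the window are possible. Take a person with bariatric surgery more than a month ago.

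- *Window on the surgery.* Older surgery is not among the named examples. If the person reports significant malabsorption, the opening clause can still exclude them, because the list is illustrative. If not, they are eligible.
- *Window on the malabsorption.* Malabsorption in the last month excludes, whatever the date of surgery. Without it, the person is eligible.
- *Window on the whole list.* As above, and it is also unclear whether celiac disease or chronic diarrhea outside the last month counts.

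The person with older surgery and no reported, significant malabsorption passes in all three cases, because the criterion turns on reported malabsorption and not on the operation.

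**Profiles per dose.** Statistical Considerations describes "three subjects in each of three treatment sequences in each of two cohorts". Under Clinic Visits, serial sampling takes place at Visit 1. In Table 1, two of the three sequences in each cohort give the profiled dose at Visit 1, so 2 × 3 = 6 at 150 mg and 6 at 600 mg. This reproduces the stated n=6. If sampling followed the dose instead, as the Pharmacokinetic Testing paragraph could be read, the count would be 3 × 3 = 9.

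**Effect of one affected subject.** Let r be that subject's exposure relative to normal. The documents give no value, so r = 0.7, 0.5 and 0.3 are assumptions. The other subjects are set to 1. The plan calculates means of the individual parameters, so the arithmetic mean is used first.

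| r | Mean AUC, n=6: (r−1)/6 | Mean Dose/AUC, n=6: (1/r−1)/6 | Mean AUC, n=9: (r−1)/9 |
|---|---|---|---|
| 0.7 | −5.0% | +7.1% | −3.3% |
| 0.5 | −8.3% | +16.7% | −5.6% |
| 0.3 | −11.7% | +38.9% | −7.8% |

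Under true proportionality with n=6, the dose-normalized 600:150 ratio of mean AUCs would move from 1 to 0.950, 0.917 or 0.883 if the subject is in the 600 mg group. It would move to 1/0.950 = 1.053, 1/0.917 = 1.091 or 1/0.883 = 1.132 if the subject is in the 150 mg group.

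**Against sampling error.** The documents give no between-subject CV for AUC, so 20, 40 and 60% are assumed. The relative standard error of the comparison is about CV × √(1/6 + 1/6) = 0.577 × CV, or 11.5, 23.1 and 34.6%. The r = 0.5 shift of 8.3% is then 0.72, 0.36 and 0.24 standard errors. The worst combination, r = 0.3 with a 20% CV, is 11.7/11.5 = 1.0.

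On a log scale, which the plan does not specify, the 150-to-600 mg slope shifts by ln(r)/6/ln(4) = −0.043, −0.083 or −0.145. Its standard error, √(2/6) × √ln(1+CV²)/ln(4), is 0.082, 0.16 or 0.23. The r = 0.5 case is about 1.0, 0.5 and 0.36 standard errors. The worst combination reaches about 1.8.

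**Chance that it happens.** Prevalence among recruits is not given. If a proportion p of enrollees were affected, the chance of at least one among the 12 profiled subjects is 1 − (1−p)^12, which is 11.4% for p = 1%, 21.5% for 2% and 46.0% for 5%. These values of p are illustrations only.

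**The case against.** A reader might infer that anyone operated on two months or five years ago is simply eligible, malabsorption or not. The documents do not support that. The examples are illustrative, so someone reporting significant malabsorption from old surgery can be excluded under the opening clause, and the window may in any case attach to the malabsorption. This part of the objection stands and narrows the gap to people without reported, significant malabsorption.

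Other filters also exist: laboratory abnormalities that the medical investigator judges significant, long-term medication use, the description of subjects as healthy, and medical history taken by phone and at screening. They would stop some of these people. None names past surgery, and each is partial, incidental or discretionary, so they reduce the gap without closing it.

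The size is conditional on an assumed loss of absorption and an unknown prevalence, and in most of the range examined it lies within sampling error. In addition, with sampling at Visit 1 only, an affected subject in Sequence 3 or 6 receives placebo at that visit and contributes no full active-dose profile. All of this stands, and it limits how much weight the point can carry.

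**Conclusion.** The point holds in a narrow form. The scope of the window is unclear, and on every reading a person with bariatric surgery more than a month ago and no reported, clinically significant malabsorption can enroll. One such subject among six profiles would lower that dose group's arithmetic mean AUC by about 5, 8 or 12% if exposure were 70, 50 or 30% of normal. This is modest against between-subject variation at the CVs assumed.

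It would be tempting to conclude that the proportionality assessment is invalid or the primary objective compromised. The documents do not show either. The quantified effect falls on the secondary objective. An under-absorbing subject would also be less exposed at both active doses, as one of nine in the cohort's tolerability review, but the documents give no basis for putting a figure on that. The case for acting is that the limit is unexplained and easy to remove, not that a large bias is expected.

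**What to change.** Delete the one-month window and split the criterion into two:

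- (a) any history of bariatric surgery, or of other gastric or intestinal resection or bypass, at any time;
- (b) "Reported clinically significant GI malabsorption syndromes such as chronic diarrhea" or celiac disease.

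Part (a) then turns on the operation itself and needs no judgement about symptoms. Part (b) keeps the present threshold of reported and clinically significant. Check both against the medical history already taken by phone and at the screening visit. If the sponsor intends people with older bariatric surgery to be eligible, the protocol should say so, state what the window limits and give the reason.

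The cost is one reworded criterion and a few volunteers not enrolled. No procedure or visit is added, and the planned 18 subjects and six profiles per dose are unchanged.
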